2.5 Treatment Assignment and Blinding

The study will be “masked” or “blinded” in the sense that all the study subjects and the study team members will be blinded to the assignment in the study groups. Only the pharmacist who will prepare the study drug kits and the unblinded statistician will have access to the kit assignments. The Medical Monitor will be contacted. A copy of the randomization list with study ID assignments will be saved in a limited access folder on a secure network server at Pharm-Olam. The Medical Monitor will be contacted in emergent medical cases when knowing the treatments assignment is mandatory for clinical care of the study subject.

The data will be presented without having the treatment assignments of individual study subjects made known to study team members including the study PI. Table shells will be blinded. If DSMB members find any safety issues, they may request specific unblinded data. Table shells for DSMB (content and formats) will be agreed upon prior to start of study.

Subjects will receive one time dose of oral ZNS or matching placebo after training if TTS is identified on audiogram 5-30 minutes after shooting. Subjects will be instructed to take study drug without food. We will recommend that capsules be swallowed whole per the current approved labeling.

2.6 Schedule of Assessments and Procedures

The table below summarizes the calendar of study activities and assessments

	VISIT 1 Screening Assessment	VISIT 2 Baseline Assessment	Post-training		
			VISIT 3 Within 5-30 Minutes	VISIT 4 Within 24 Hours	VISIT 5 30 days (+/- 3 days)***
Informed Consent	X				
Demographic Info	X				
Current Meds	X				
Questionnaires	X				X
Cognitive Assessment		X		X	
Clinical ear exam	X	X	X		X
Audiogram	X	X	X		X
ECochG		X			X
DPOAE		X	X		X
WIN		X			X
Sound Measurements	X	X	X		X
Randomization			X*		

	VISIT 1 Screening Assessment	VISIT 2 Baseline Assessment	Post-training		
			VISIT 3 Within 5-30 Minutes	VISIT 4 Within 24 Hours	VISIT 5 30 days (+/- 3 days)***
Oral Dose* ZNS or Placebo			X*		
Blood draw**		X		X	
AE Assessment			X	X	X

* Dispensed after training if TTS is identified on audiogram 5-30 minutes after shooting.

** Blood draw: Electrolyte panel, BUN, Cr, ALT, and AST; DNA analysis and serum pregnancy test at baseline

***If TTS is seen from pure tones after each training session

2.7 Sample Size Determination for The Primary Efficacy Outcome Measure

Calculation of sample size for this study is based on a balanced design and a one-sided significance level of 0.025. We estimate that among officers identified as being at high risk for permanent hearing loss due to having TTS, the proportion of PTS positive officers 30 days (+/- 3 days) after shooting will be 50%. This is the proportion of PTS positive officers we expect to observe in the placebo group. Thus, for the primary outcome, we estimated that 66 officers per group will provide us with 80.5% power to detect a 50% reduction in the proportion of PTS positive officers (from 50% to 25%) at the 1-sided alpha level of 0.025. A planned total of 132 subjects is to be enrolled and randomized.

We will make all the needed efforts to eliminate drop outs, and due to short term-follow-up of the study subjects in a period we do not expect any drop-outs or lost to follow-up.

All sample size calculations were carried out using PROC POWER procedure in SAS 9.4.

3 Study Outcomes

3.1 Primary estimand

The primary estimand for the study is: In police officers who are training for firearm certification as part of their standard occupational requirements and suffer temporary threshold shift (TTS) following shooting range noise exposure, what is the difference in the proportion of officers experiencing PTS (defined as all officers who in audiogram are identified as having a permanent threshold shift (PTS) of ≥ 10 dB HL increase at any frequency from 2-6 kHz in at least one ear (30 days (+/- 3 days) post shooting - Baseline) to total number of subjects in each study arm/group) between ZNS treatment compared to Placebo, 30±3 days after randomization.

3.2 Primary Efficacy Outcome

The primary efficacy outcome will be the proportion of PTS positive subjects defined as the ratio of PTS-positive subjects to total number of subjects in each study arm/group. PTS positive will be defined as all subjects who in audiogram are identified as having a permanent threshold shift (PTS) of ≥ 10 dB HL increase at any frequency from 2-6 kHz after shooting as compared to baseline audiogram. A SAS code will be written to code as PTS positive all the officers for whom the difference at any frequency from 2-6 kHz in hearing thresholds (30 days (+/- 3 days) post shooting - Baseline) will be ≥ 10 dB HL in at least one of the ears. If this difference is less than 10 dB then the officers will be coded as non-PTS positive.

To date, there are no reports of ZNS being associated with hearing damage or loss, so the hypothesis for this study will be a one-sided hypothesis.

For the primary outcome measure, the null and alternative hypotheses are provided below.

Comparison of the proportion of PTS-positive subjects between ZNS group and Placebo

$$H_0: p_{ZNS} - p_{Placebo} = 0 \quad H_A: p_{ZNS} < p_{Placebo}$$

We hypothesize that ZNS will reduce the proportion of PTS-positive officers by an absolute difference of 25% as compared to placebo. Our one-sided hypothesis is supported by animal studies, and lack of any evidence of hearing loss as a side effect of ZNS in human studies.

Hypothesis testing for the primary outcome will be performed at the one-sided alpha level of 0.025.

3.3 Secondary efficacy outcomes

The study is designed to test the null hypothesis associated with the primary efficacy measure. Nevertheless, it provides a great opportunity to evaluate the impact of ZNS on other audiometric and clinical measures:

- DPOAEs: Distortion product otoacoustic emissions will be measured at baseline

(before shooting), as well as within 5-10 minutes after shooting and 30 days (+/-3 days) post-shooting (for officers with positive TTS) to measure both temporary and permanent changes in DPOAE amplitude relative to baseline. A change is noted in DPOAE amplitude at any frequency that is significantly greater than the stability of each measurement (i.e., 95% confidence interval of each measurement do not overlap).

- Ultra-high frequency audiometry: Ultra-high frequency audiometry (10-14 kHz) will be measured at baseline (before shooting), 30 days (+/-3 days) after shooting (for officers with positive TTS) to measure for both temporary and permanent high frequency audiometric changes. A significant change is defined for any frequency that is greater than 5 dB HL from baseline thresholds.
- ECochG: Electrocochleography will be measured at baseline (before shooting) and 30 days (+/-3 days) after shooting (for officers with positive TTS) to measure for changes in ECochG AP amplitude, latency and width.
- WIN testing: The Words-In-Noise test will be administered at baseline (before shooting) and 30 days (+/-3 days) after shooting (for officers with positive TTS). The respective scores will be converted to Z-scores to evaluate for any change in scores relative to baseline.

3.4 Exploratory analysis

Exploratory DNA analysis and phenotypic correlations with ZNS treatment.

3.5 Safety measures

We will closely monitor and report all the AE and SAE in the study according to Institutional guidelines.

Potential side effects from the administration of ZNS:

- Somnolence
- Anorexia
- Dizziness
- Ataxia
- Agitation/irritability
- Difficulty with memory and/or concentration

ZNS may cause serious side effects, including:

- Serious skin rash that can cause death.
- Serious allergic reactions that may affect different parts of the body.
- Less sweating and increase in body temperature (fever).
- Suicidal thoughts or actions in some people.
- Increased level of acid in blood (metabolic acidosis).
- Problems with concentration, attention, memory, thinking, speech, or language.

In this study we will assess cognitive performance. Cognitive assessments will be administered within 24 hours following drug intake, testing will take \leq 20 minutes.

4 Analysis Populations

4.1 Target population

Target population includes all patients that meet the inclusion/exclusion criteria as defined in the study protocol.

4.2 Intent-to-treat (ITT) sample

ITT sample will include all subjects who are randomized. Following principles of intent-to-treat analysis all subjects will be analyzed in the treatment group they were randomized to when they were enrolled in the study.

4.3 The safety sample

The safety sample included subjects from the full analysis population who were enrolled and received active or placebo ZNS. Adherence to protocol does not affect inclusion in safety population.

4.4 Per-protocol sample

The per-protocol sample is limited to subjects who were randomized and treated in compliance with the protocol. Only observations or specimens collected according to the protocol were included in the analyses using the per-protocol population. If a subject received one or more treatments out of compliance with the protocol schedule, any observations or specimens collected after the out-of-compliance treatment were excluded from the analyses using the per-protocol population.

For this study, we have approximately 800 officers from Akron and Summit County, not including additional local police departments from which to screen and recruit, understanding a large percentage of the population may already present with significant NIHL, thus, may not meet the eligibility criteria. In a previous study by the investigators, 62-85% of police officers presented with evidence of NIHL, therefore, we need a significantly larger sample size to recruit subjects that meet our eligibility criteria. We estimate that each year we will have at least 60 officers screened within 1 hour of shooting each year. If the rate of TTS after 1 hour of shooting is that of the study from Blioskas et al, we estimate that 48 officers will qualify to undergo randomization each year. If 70% of them consent to be randomized there will be 34 officers enrolled and completing the trial each year. Based on these estimates, we will be able to meet our accrual goals and complete the study with a sample size of 132 officers in approximately 4.5 years.

5 GENERAL ASPECTS FOR STATISTICAL ANALYSES

5.1 General Methods

- All analyses and summaries will be produced using SAS® version 9.4 (or higher).
- Standard descriptive statistics will be used to describe distribution of demographic, clinical, and audiometric characteristics as well as outcome measures for all the study samples listed in section 2.5. For continuous level characteristics Q-Q plots and Shapiro-Wilk test will be used to test assumption of normality. If continuous level data is found to be normally distributed data, mean and standard deviation will be used as descriptive statistics, and if the assumption of normality is violated, we will report median and range for description of these variables. Frequency and relative frequency will be used for description of categorical level variables.
- The same number of decimal places as in the raw data will be presented when reporting range, 1 more decimal place than in the raw data will be presented when reporting the mean and median, and 2 more decimal places than in the raw data will be presented when reporting the standard deviation.
- Unless stated otherwise, tabular summaries will present columns for the active treatment arm (“ZNS (100 mg PO)”), placebo arm, and overall.
- Unless stated otherwise, the relative frequency will be based on the number of non-missing observations. The column header will still contain the number of subjects in the treatment group. There will be a row for the number of non-missing observations in the table (at each time point, if required) for each variable being summarized.
- Any calculated p-values will be presented to 3 decimal places; p-values less than 0.001 will be presented as ‘p<0.001’ and p-values greater than 0.999 will be presented as ‘p>0.999’.
- All relevant subjects data will be included in listings and sorted by treatment group, Participant ID, and visit, as applicable, for all randomized subjects.
- Unscheduled or repeat assessments will not be included in summary tables unless specified. All assessments will be included in the participant listings.
- All tables, listings and figures will include footers that identify the name of the program that created the output, together with the date and time on which it was created. Headers will include the total number of pages that the presentation contains and, for each page, the number of the page within the presentation.

5.2 Missing Data

Every attempt will be made to ensure data completeness. We do not anticipate much loss to follow-up because of the relatively short time follow-up interval. Conservatively, we would estimate that fewer than 5% of subjects will drop out/withdraw from the study. The participant will be withdrawn from the study follow-up and procedures if the participant withdraws consent, or the sponsor decides to close the study.

Data loss, if any, would almost likely be due to subjects refusing to complete or not returning at all for the post-shooting assessment of PTS 30 days (+/- 3 days). If the subject reschedules the post-shooting appointment for a later date for any reason, and if this delay is within 30 days of the scheduled date, the data will be considered valid and used in the efficacy analysis. Any measure outside this time window of +30 days will be defined and considered as missing data.

Missing PTS at 30 days will be imputed using SAS PROC MI procedure within each treatment group using the distribution implied by the non-missing data for the specific treatment group. The SAS code below using MICE via the Fully Conditional Specification (FCS) statement will be used to impute the missing data under the missing at random (MAR) assumption.

```
PROC MI DATA=X SEED=<value> NIMPUTE=10 OUT=MI_OUT1 NOPRINT;
  CLASS GROUP;
  VAR AGE PTA LSurg....;
  FCS LOGISTIC(PTS);
  RUN;
```

The estimates of the analysis of the 10 imputed datasets will be then combined following Rubin's rules using PROC MIANALYZE procedure in SAS which will be of the form:

```
PROC MIANALYZE PARMs=GMPARMS COVB=GMCOVB PARMINFO=GMPINFO WCOV BCOV
  TCOV; / *dataset "gmparms" contains the estimates and associated standard errors
  for the mean parameters from each of the M=10 imputed data sets.
  dataset "gmcovb" contains the asymptotic covariance matrices
  dataset "gmpinfo" contains parameter info*/
  MODELEFFECTS group;
  RUN;
```

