### **Missing Data**

Every attempt will be made to ensure data completeness. We do not anticipate much loss to follow-up because of the relatively short time follow-up interval. Conservatively, we would estimate that fewer than 5% of subjects will drop out/withdraw from the study. The participant will be withdrawn from the study follow-up and procedures if the participant withdraws consent, or the sponsor decides to close the study.

If any, the loss of data would almost certainly be due to the fact that the subjects refused to complete or did not show up for the assessment of PTS 30 days (+/- 3 days) after the baseline assessment on shooting day. If the subjects reschedule the follow-up appointment for a later date for any reason, and if this delay is within 30 days of the scheduled date, the data will be considered valid and used in the efficacy analysis. Any measure outside this time window of +30 days will be defined and considered missing data.

Missing PTS at 30 days will be imputed using SAS PROC MI procedure within each treatment group using the distribution implied by the non-missing data for the specific treatment group.

The SAS code below using MICE via the Fully Conditional Specification (FCS) statement will be used to impute the missing data under the missing at random (MAR) assumption.

```
PROC MI DATA=X SEED=<value> NIMPUTE=10 OUT=MI_OUT1 NOPRINT;
CLASS GROUP;
VAR AGE PTA LSurg.....;
FCS LOGISTIC(PTS);
RUN;
```

The estimates of the analysis of the 10 imputed datasets will be then combined following Rubin's rules using PROC MIANALYZE procedure in SAS which will be of the form:

```
PROC MIANALYZE PARMS=GMPARMS COVB=GMCOVB PARMINFO=GMPINFO WCOV BCOV
TCOV; / *dataset "gmparms" contains the estimates and associated
standard errors for the mean parameters from each of the M=10 imputed
data sets.
dataset "gmcovb" contains the asymptotic covariance matrices
dataset "gmpinfo" contains parameter info*/
  
MODELEFFECTS group;
RUN;
```

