### **Noise Exposure Group Assignment Based on Interview Questions**

- Participants with a response to 1.A., 2.A., or 3.A. of monthly or more frequent exposure are assigned to the higher noise group. Participants with less than monthly exposure are assigned to the lower noise group.
- Participants with a response to 1.C., 2.C, or 4.C. of 5 years or more are assigned to the Higher Noise group.

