7.1.1 Analysis of primary outcome variable

Efficacy analysis at the end of the study

The primary outcome measure for assessing effectiveness of ZNS (100 mg PO) post-shooting compared to the placebo group will be the proportion of officers with TTS defined as PTS positive 30 days (+/- 3 days) after shooting range exposure.

Audiogram will be performed to look for PTS. Officers for whom the difference at any frequency from 2-6 kHz in hearing thresholds (30 days (+/- 3 days) post-shooting - Baseline) is ≥ 10 dB HL will be defined as PTS positive. Primary analysis and sensitivity analyses will be carried out on the primary endpoint.

Primary analysis

Frequency and relative frequency will be used to describe the distribution of the primary outcome measure in each study group. To assess efficacy, Fisher's exact test will be used to compare the proportion of officers with PTS positive in ZNS group with the proportion of officers with PTS positive in the placebo group.

The confidence intervals will be calculated using method 10 described by Newcombe RG, 1998 and also described by Altman et al.

1. Altman, Douglas, et al., eds. Statistics with confidence: confidence intervals and statistical guidelines. <https://www.amazon.com/Statistics-Confidence-Intervals-Statistical-Guidelines/dp/0727913751>

Let n_1 be the number of participants in placebo group, and r_1 the number of participants with PTS in the placebo group. $p_1=r_1/n_1$ be the proportion of PTS in the placebo group, and q_1 the proportion of participants that do not have PTS in placebo group.

l_1 and u_1 are the lower and upper limits of the $100(1-\alpha)\%$ confidence interval for p_1

Using Wilson method we calculate:

$$A_1 = 2r_1 + z^2$$

$$B_1 = z\sqrt{z^2 + 4r_1 q_1}$$

$$C_1 = 2(n_1 + z^2)$$

$$l_1 = \frac{(A_1 - B_1)}{C_1} \quad u_1 = \frac{(A_1 + B_1)}{C_1}$$

z_α = the $100(1 - \alpha)^{th}$ percentile of the standard Normal distribution.

Let n_2 be the number of participants in ZNS group, and r_2 the number of participants with PTS in the ZNS group. $p_2 = r_2/n_2$ be the proportion of PTS in the ZNS group, and q_2 the proportion of participants that do not have PTS in ZNS group.

l_2 and u_2 are the lower and upper limits of the $100(1-\alpha)\%$ confidence interval for p_2

$$A_2 = 2r_2 + z^2$$

$$B_2 = z\sqrt{z^2 + 4r_2q_2}$$

$$C_2 = 2(n_2 + z^2)$$

$$l_2 = \frac{(A_2 - B_2)}{C_2} \quad u_2 = \frac{(A_2 + B_2)}{C_2}$$

The proportion difference between groups is: $D = p_1 - p_2$

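### The PTS endpoint is defined at 30 ± 3 days, but the missing-data rule accepts audiograms up to 30 days late, so the primary analysis does not measure the stated estimand.

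*SAP*

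**What the plan says.** SAP 3.1 defines the estimand as the difference in PTS proportions "between ZNS treatment compared to Placebo, 30±3 days after randomization". SAP 3.2, which specifies the coding of PTS, and SAP 7.1.1 use 30 ± 3 days after shooting. Protocol 6.0, 12.1 and 12.2.1 do the same, and both visit calendars place Visit 5 there.

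SAP 5.2 then deals with a subject who reschedules, for whatever reason: "if this delay is within 30 days of the scheduled date, the data will be considered valid and used in the efficacy analysis". Only an audiogram later than that counts as missing. The Missing Data text in protocol 12.2.2 has the same rule, with the same condition: "if this delay is within 30 days of the scheduled date".

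Two sensitivity analyses are planned (SAP 7.1.1), and both concern how missing values are imputed. All efficacy analyses are also run in the per-protocol sample (SAP 7), which keeps only observations collected according to the protocol (SAP 4.4).

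**The concern.** The two rules give different answers for the same officer. Under SAP 3.2 a day-45 audiogram is outside the endpoint, so the outcome would be missing and imputed. Under SAP 5.2 it is an observed primary outcome. The acceptance rule governs what enters the efficacy analysis, so the quantity estimated is PTS at some time between day 27 and about day 60, not PTS at 30 ± 3 days.

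The extra time matters because of the population. Protocol 1.5 describes police officers as repeatedly exposed to continuous and impulse noise, while the objective concerns PTS after the range session that caused the temporary shift. One new shift of 10 dB at one frequency in one ear makes an officer positive. An audiogram near day 60 covers about twice the interval of an on-time one, and the plan cannot separate a new injury from the index injury. The Visit 5 noise screen (protocol Appendix H) asks only about the preceding 30 days, so at day 60 it misses roughly the first month. No planned model uses it.

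**Working it through.** **Windows.** Stated: days 27 to 33, which is 33 − 27 + 1 = 7 days. Accepted: days 27 to about 60, which is 60 − 27 + 1 = 34 days, reaching 60 − 33 = 27 days past the stated upper limit. If the visit had been scheduled for day 33, the limit would be day 63.

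**Inputs from the plan.**
- SAP 2.7: "Calculation of sample size for this study is based on a balanced design and a one-sided significance level of 0.025".
- SAP 2.7: "66 officers per group will provide us with 80.5% power", for PTS rates of 50% on placebo and 25% on zonisamide (ZNS).
- SAP 7.1.1: Fisher's "exact test will be used to compare the proportion of officers with PTS positive in ZNS group" with that in the placebo group.

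**Reproducing the plan's power.** The arcsine approximation to Fisher's test with continuity correction is

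power = Φ{√(2n) · [asin√(p₁ − 1/2n) − asin√(p₂ + 1/2n)] − 1.96}.

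With n = 66, p₁ = 0.50 and p₂ = 0.25 it gives 80.5%, the stated figure. Full enumeration of the one-sided Fisher test at 0.025 gives 81.3%. That is the reference below.

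**Effect of keeping late audiograms.** Two quantities are needed, and the documents give neither:
- f, the share of each arm tested late;
- q, the share of late-tested officers, otherwise PTS-negative, who become positive from new noise.

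Both are assumed equal in the two arms. Then

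- p(placebo) = 0.50 + 0.50·f·q
- p(ZNS) = 0.25 + 0.75·f·q
- difference = 0.25·(1 − f·q)

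| f | q | Placebo | ZNS | Difference (points) | Fisher power |
|---|---|---|---|---|---|
| 0 | – | 50.0% | 25.0% | 25.0 | 81.3% |
| 5% | 10% | 50.25% | 25.4% | 24.9 | 80.7% |
| 10% | 10% | 50.5% | 25.75% | 24.75 | 80.1% |
| 20% | 20% | 52.0% | 28.0% | 24.0 | 76.2% |
| 30% | 30% | 54.5% | 31.75% | 22.75 | 69.3% |

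**Effect of discarding late audiograms instead.** Complete-case analysis at the planned rates, with 66·(1 − f) rounded down:

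| Late share | Per arm | Fisher power |
|---|---|---|
| 5% | 62 | 78.3% |
| 10% | 59 | 75.4% |
| 20% | 52 | 70.3% |

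At 10% late and 10% conversion, keeping the late data (80.1%) costs less power than dropping them (75.4%).

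**Is the effect visible in any planned analysis?** Neither sensitivity analysis restricts to days 27–33. The per-protocol sample might, because the calendar puts Visit 5 at 30 ± 3 days. But the protocol itself calls the late audiogram valid, so one can argue it was collected according to the protocol. Its status is undefined.

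**The case against.** The late rule can be defended as an ordinary arrangement: a narrow target for the visit and a wider window for the analysis. It is explicit, pre-specified and alike in both documents, it follows directly on a sentence naming the 30 ± 3 day assessment, and protocol 5.4 warns that follow-up times may vary. So a reader who inferred that the window is widened silently would be wrong. What is missing is agreement with the estimand, and that part of the concern stands.

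The construct is also largely preserved. Protocol 1.2 says PTS is measured two to three weeks after exposure, so without new injury a late audiogram still measures PTS. New noise can act within days 0–33 too; the late rule widens an attribution gap that already exists. Both arguments limit the size of the problem without removing the mismatch.

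Three stronger readings are tempting, and the documents do not support them:

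- *High Noise officers are by definition exposed at least monthly, so late audiograms must carry new noise.* Appendix G does say that participants with "monthly or more frequent exposure are assigned to the higher noise group", but five or more years on the duration items is a second route into that stratum. The military item asks about past service. The stratum does not establish exposure after dosing; protocol 1.5 supports only the weaker statement that officers are repeatedly exposed.
- *Every late officer is misclassified.* If 5–10% of 132 attend late, that is 6.6 to 13.2 officers tested off-window. At the planned rates (0.50 + 0.75)/2 = 62.5% of them are negative; if 10% of those convert, 13.2 × 0.625 × 0.10 ≈ 0.8 officers change status at the upper end.
- *The rule inflates the type I error.* It is the same in both blinded arms, and equal contamination moves the two rates closer together.

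**Conclusion.** Wrong as written, and it should be corrected. The estimand, outcome definition and primary analysis name one window and the missing-data section applies another, so the primary analysis as specified does not estimate the stated quantity. That conclusion needs no assumption.

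The size does rest on assumptions. With late attendance and conversion equal in both arms, the loss is about one point of power at 10% and 10%, about 5 points at 20% and 20%, and 12 points at 30% and 30%. If few officers attend late, the numerical effect is small, and the main harm is that a result labelled 30-day is not one. The expected direction is dilution, against finding an effect.

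**What to change.** State one analysis window, in days since shooting, in SAP 3.1, 3.2, 5.2 and 7.1.1 and in the protocol's Missing Data text and endpoint sections. Two routes are coherent:

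1. **Lower cost.** Keep late audiograms in the primary analysis, restate the estimand window to match (days 27 to about 60, with a fixed upper day), and add a pre-specified sensitivity analysis restricted to days 27–33.
2. **Alternative.** Keep days 27–33 as primary, treat later audiograms as missing but use them as auxiliary data in the imputation, and add a sensitivity analysis that accepts them. Simply dropping them would incur the complete-case losses shown above; the auxiliary data may recover part of that.

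Under either route, state in SAP 4.4 that the per-protocol sample includes only audiograms from days 27–33.

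The cost is wording in both documents and one extra analysis. Route 1 also means a wider stated time point. No new data are needed beyond the audiogram date.
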